OS for each arm will be summarized using Kaplan Meier curves and further characterised in terms of the median and survival probabilities at 6, 12 and 18 months along with the corresponding 2-sided 95% CI for the estimates.

The hazard ratio of OS with its 95% confidence interval will be estimated with a stratified Cox proportional hazard model (stratification factors based on IWRS data).

For missing data (not linked to intercurrent events), *i.e.* participants without documentation of death (lost to follow-up, withdrawal of consent, administrative end of study), the OS will be censored on the last contact date the participant was known to be alive or the cut-off date, whichever is earlier.

Sensitivity analyses

As sensitivity analyses, the following analyses will be done:

- The proportional hazards assumption will be checked. If relevant, other statistical method could be used.
- OS analysis based on PPS.

Other sensitivity analyses will be defined in the SAP if necessary.

Supplementary analyses

Subgroup analyses

OS subgroup analyses are planned to further explore the homogeneity of the treatment effect across participant subsets. Depending on the sample size, the following subgroups will be examined: ECOG PS (0, 1), extracellular domain EGFR mutations (ECD) (presence, absence), previous regimens of treatment (2, \geq 3), region (North America, European Union, Asia, Rest of the World), time since diagnosis of 1st metastasis (< 18, \geq 18 months), location of primary disease (right, left), gender (female, male), age (< 70, \geq 70 years), prior surgical resection (yes, no), number of metastatic sites (1-2, \geq 3), neutrophils to lymphocytes ratio (NLR < 3, NLR \geq 3), neutrophils to lymphocytes ratio (NLR < 5, NLR \geq 5), response to previous treatment with anti-EGFR (CR/PR, SD), last previous regimen (anti-EGFR, no anti-EGFR), previously treated with anti-VEGFs treatment (yes, no), skin toxicity with previous anti-EGFR (yes, no), skin toxicity with previous anti-EGFR (Grade 1-2, Grade 3-4, no toxicity), duration of previous anti-EGFR (< 8, \geq 8 months), Race (White, American Indian/Alaska native, Asian, Black/African

American, Native Hawaiian/Other pacific islander), Premedication with antibiotics for skin toxicity (yes, no).

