A stratified Cox-regression model with treatment arm as predictor variable will be fitted separately for each subgroup category. The hazard ratio for treatment along with the associated 95% confidence interval will be provided.

Exploratory analysis

A multivariate OS analysis will be performed using a stratified Cox proportional hazard model (3 stratification factors (ECOG PS (0 *versus* 1), extracellular domain EGFR mutations (ECD) (presence *versus* absence) and previous regimens of treatment (2 *versus* ≥ 3)). Treatment will be included in the model and a stepwise selection process (p-value to enter < 0.15 , p-value to remain < 0.10) will be applied to identify potential additional prognostic factors among the following covariates: region (North America, European Union, Asia, Rest of the World), time since diagnosis of 1st metastasis (< 18 , ≥ 18 months), location of primary disease (right, left), gender (female, male), age (< 70 , ≥ 70 years), prior surgical resection (yes, no), number of metastatic sites (1-2, ≥ 3), neutrophils to lymphocytes ratio (NLR < 3 , NLR ≥ 3), neutrophils to lymphocytes ratio (NLR < 5 , NLR ≥ 5), response to previous treatment with anti-EGFR (CR/PR, SD), last previous regimen (anti-EGFR, no anti-EGFR), previously treated with anti-VEGFs treatment (yes, no), skin toxicity with previous anti-EGFR (yes, no), skin toxicity with previous anti-EGFR (Grade 1-2, Grade 3-4, no toxicity), duration of previous anti-EGFR (< 8 , ≥ 8 months), Race (White, American Indian/Alaska native, Asian, Black/African American, Native Hawaiian/Other pacific islander), Premedication with antibiotics for skin toxicity (yes, no).

10.1.2.4.2.2. Key secondary estimand based on the OS

The key secondary estimand of interest is the effect of the randomised treatments on the survival duration in all subjects that are KRAS/NRAS, BRAF WT and EGFR-extracellular domain WT (Triple negative [TN]) regardless of whether or not intercurrent events occur (treatment policy strategy). The motivation for this choice is to assess the efficacy of the futuximab/modotuximab in combination with trifluridine/tipiracil compared to trifluridine/tipiracil monotherapy under the ITT principle (intercurrent events are considered to be part of the treatments being compared).

All data collected during the trial regardless of occurrence of an IE will be used. This is aligned with the treatment policy strategy.

The following analyses will be done as primary analyses:

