- The distribution of OS will be compared between the two treatment groups using a stratified log-rank test at one-sided 2.5% level of significance (stratification factors based on IWRS data).
- OS for each arm will be summarized using Kaplan Meier curves and further characterised in terms of the median and survival probabilities at 6, 12 and 18 months along with the corresponding 2-sided 95% CI for the estimates.
- The hazard ratio of OS with its 95% confidence interval will be estimated with a stratified Cox proportional hazard model (stratification factors based on IWRS data).

As OS in TN population is identified as the key secondary estimand, closed sequential testing procedure will be used to statistically evaluate and interpret OS in TN population only if the

primary estimand, OS in DN population, is statistically significant. Therefore, the family-wise error rate is strongly controlled.

The following analyses will be done as sensitivity analyses:

- The proportional hazards assumption will be checked. If relevant, other statistical method could be used.
- OS analysis based on PPS.

Other sensitivity analyses will be defined in the SAP if necessary.

For missing data (not linked to intercurrent events), *i.e.* participants without documentation of death (lost to follow-up, withdrawal of consent, administrative end of study), the OS will be censored on the last contact date the participant was known to be alive or the cut-off date, whichever is earlier.

The same subgroup analyses as used for the primary estimand will be done.

10.1.2.4.2.3. Supplementary estimand based on OS

One supplementary estimand based on OS is defined in order to assess the effect of the randomised treatments on the survival time in all subjects who are KRAS/NRAS and BRAF WT (Double negative [DN]) before participants receive further anti-cancer therapy (while on treatment strategy).

The other estimand based on OS is defined in order to assess the effect of the randomised treatments on the survival time in all subjects who are KRAS/NRAS, BRAF WT and EGFR-extracellular domain WT (Triple negative [TN]) before participants receive further anti-cancer therapy (while on treatment strategy).

The aim of this estimand is to evaluate the effect of the study treatment without a potential effect of another therapy.

The use of data post intercurrent events will be different according to the IE:

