- The hazard ratio of PFS with its 95% confidence interval will be estimated with a stratified Cox proportional hazard model (stratification factors based on IWRS data).

The following analyses will be done as sensitivity analyses:

- An analysis that considers clinical progression and administration of further anti-cancer therapy as PFS events in addition to the radiological progression or death.
- PFS analysis based on PPS.

For missing data (not linked to intercurrent events), *i.e.* participants who were lost to follow-up or who have withdrawn their consent without radiological progression or reached the time point of analysis without a known record of death or radiological progression, the PFS will be censored at the date of last evaluable tumour assessment or the cut-off date, whichever is earlier.

The same subgroup analyses as used for the primary estimand will be done for PFS.

Secondary estimands based on ORR and DCR

Other secondary estimand of interest are the effect of the randomised treatments on response in all subjects before participants receive further anti-cancer therapy.

Responses recorded after intercurrent event will be excluded. This is aligned with the estimand and the treatment while on treatment strategy.

The following analyses will be done:

- OR based on the investigator's tumour assessment will be compared in the FAS between treatment arms using a stratified Cochran-Mantel-Haenszel (CMH) test. A 2-sided 95% CI for the difference in ORR between the two treatment arms will also be provided based on the normal approximation. If required, a Fisher's exact test and 2-sided 95% Clopper-

Pearson CIs will be used. A 2-sided 95% CI for the difference in ORR between the two treatment arms will also be provided based on the normal approximation.

- DC based on the investigator's tumour assessment will be compared in the FAS between treatment arms using a stratified CMH test. A 2-sided 95% CI for the difference in DCR between the two treatment arms will also be provided based on the normal approximation. If required, a Fisher's exact test and 2-sided 95% Clopper-Pearson CIs will be used. A 2-sided 95% CI for the difference in DCR between the two treatment arms will also be provided based on the normal approximation.

Secondary estimands based on DoR, TTNT, TTR and TtPS2

Responses recorded after intercurrent event will be excluded. This is aligned with the estimand and the treatment while on treatment strategy.

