10.2. Determination of sample size

Approximately 25 participants will be evaluated in Safety Lead-In part. The DMC will initially determine tolerability after 6 evaluable participants have been treated. If ≤ 2 participants out of the first 6 experience a DLT, and the DMC based on the totality of safety data determines the doses to be tolerable, then the Safety Lead-In will be expanded by an additional cohort of 6 participants. The DMC will again assess the tolerability when 12 participants have been enrolled and the 12th participant has completed the first treatment cycle. If ≤ 3 participants experience a DLT, and the DMC based on the totality of safety data determines the doses to be tolerable, the Safety Lead-In will be expanded to add another 13 participants, for a total of 25 participants. The DMC will meet again at the end of the Safety Lead-In part when approximately 25 participants have been treated.

The primary endpoint of Randomised part will be OS in DN population, the key secondary endpoint will be OS in TN population. The primary hypothesis will test whether treatment with trifluridine/tipiracil in combination with futuximab/modotuximab compared with trifluridine/tipiracil alone leads to OS prolongation in DN population. A total of 500 patients will be randomised in a 1:1 ratio to the 2 treatment arms and followed-up until at least 383 OS events are observed across the 2 treatment arms will provide 90% power to detect a true hazard ratio (HR) ≤ 0.71 (median OS: 8.5 *vs* 12 months) using a stratified log-rank test (stratified by Performance Status [PS] [0 *vs* 1], extracellular domain EGFR mutations [extracellular domain (ECD)] [presence *vs* absence] and previous regimens of treatment [2 *vs* ≥ 3]), with an overall 1-sided significance level of 0.025 for the primary endpoint (adjusted for OS interim analyses). Assuming enrolment over 21 months with a ramp-up to a maximum of 30 patients per month and a lost-to-follow-up rate of 7% across both treatment arms, the timing of the primary analysis is expected to be at 37.5 months after 1st randomisation.

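### The OS subgroup analyses are meant to explore homogeneity of the treatment effect, but the protocol plans only separate per-category hazard ratios and no estimate that compares categories

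*Protocol*

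**What the plan says.** Protocol section 10.1.2.4.2.1, under supplementary analyses, states the purpose: "OS subgroup analyses are planned to further explore the homogeneity of the treatment effect across participant subsets". The list that follows is introduced with a condition, "Depending on the sample size, the following subgroups will be examined", and names 20 factors. Seventeen have two levels; region has four, skin-toxicity grade three and race five. ECD mutation status is among them.

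The method is one sentence: "A stratified Cox-regression model with treatment arm as predictor variable will be fitted separately for each subgroup category". The output is one more: "The hazard ratio for treatment along with the associated 95% confidence interval will be provided". There is no treatment-by-factor term, heterogeneity test, subgroup p-value, multiplicity statement or rule for reading the results. The multivariate Cox analysis in the same section selects prognostic covariates and has no treatment interaction.

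The plan is reused for OS in the TN population (section 10.1.2.4.2.2: "The same subgroup analyses as used for the primary estimand will be done") and for progression-free survival (section 10.1.2.4.2.4: "The same subgroup analyses as used for the primary estimand will be done for PFS").

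The SAP supplied is version 2.0. Its section 1 says that the randomised part was cancelled, and its section 2.3 on subgroups is marked not applicable.

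**The concern.** Homogeneity is a statement about differences between categories. The planned output describes each category alone, so the quantity that addresses the aim is not among the planned results. A reader of the resulting table or forest plot is left to compare intervals by eye. The commonest shortcut, noting which intervals exclude 1, mostly reflects how many deaths fall in each category, not whether the effect differs.

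The gap matters most for ECD status, which is a stratification factor and the only characteristic separating the primary DN population from the key secondary TN population. DN is TN plus the ECD-mutated participants, so a positive result in both does not show whether the ECD-mutated benefit to a different degree. The ECD contrast in DN would address that directly, and it is not planned. The repeat of the subgroup list in TN cannot supply it, because nobody in TN has the mutation.

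**Working it through.** **Inputs from the protocol (section 10.2).** 383 deaths ("followed-up until at least 383 OS events are observed across the 2 treatment arms"), 1:1 allocation, one-sided alpha 0.025, target HR 0.71 (medians 8.5 and 12 months; 8.5/12 = 0.708), stated power 90%.

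**Assumption.** The share q of deaths in each category is not given in either document. I use two-level splits from 50:50 to 80:20, with 90:10 as an extreme.

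**Step 1: reproduce the plan's power.** The Lan-DeMets O'Brien-Fleming function gives z = 2.511 at 255 events and 1.993 at 383, matching Table (10.2) 1. Simulation with that table's efficacy and futility bounds gives power of 89.7% at HR 0.71 and 90.0% at HR 8.5/12. The stated 90% is confirmed.

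**Step 2: chance that one category's CI excludes 1 in favour of the combination.** With SE(log HR) = 2/√(383q), this is P(q) = Φ(|ln HR|·√(383q/4) − 1.96). For HR 0.71, |ln HR| = 0.3425.
- q = 0.5: 0.3425 × √47.875 = 2.370; Φ(0.410) = 66%.
- q = 0.8: 0.3425 × √76.6 = 2.998; Φ(1.038) = 85%.
- q = 0.2: 0.3425 × √19.15 = 1.499; Φ(−0.461) = 32%.

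**Step 3: chance that exactly one of two CIs excludes 1 under a uniform effect.** The categories are disjoint, so this is P1(1 − P2) + P2(1 − P1).
- 50:50: 2 × 0.659 × 0.341 = 45%.
- 80:20: 0.850 × 0.678 + 0.322 × 0.150 = 62%.

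| Split | Power, larger / smaller level | Exactly one CI excludes 1 |
|---|---|---|
| 50:50 | 66% / 66% | 45% |
| 60:40 | 74% / 56% | 47% |
| 70:30 | 80% / 45% | 53% |
| 80:20 | 85% / 32% | 62% |
| 90:10 | 89% / 18% | 75% |

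Using 8.5/12 instead of 0.71 leaves the last column unchanged to the nearest percent. Given overall success at the final boundary (z > 1.993), the 50:50 to 80:20 range becomes 47-66%.

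**Step 4: sensitivity to the true uniform HR (50:50 to 80:20).** HR 0.60: 11-39%. HR 0.65: 26-53%. HR 0.75: 50-61%. HR 0.80: 45-50%. HR 1.0: 5%.

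**Step 5: other ways of reading the same output at HR 0.71 (50:50 to 80:20).** At least one point estimate above 1: 2-7%. Non-overlapping 95% CIs: 0.6-0.8%. Interaction test at two-sided 5%: 5% by construction.

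**Step 6: what an interaction test could detect.** The SE of the difference in log HRs is √(4/(383q) + 4/(383(1 − q))), which is 0.204 at 50:50 and 0.255 at 80:20. For 80% power the ratio of HRs must be exp[(1.96 + 0.842) × SE]: 1.77 at 50:50, 1.87 at 70:30 and 2.05 at 80:20. With 20 tests at 5%, one false positive is expected (20 × 0.05), and the chance of at least one would be 1 − 0.95^20 = 64% if they were independent, which they are not.

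**The case against.** The strongest reply is that the protocol plans no significance reading by subgroup. The analysis is supplementary, conditional on sample size, and reports estimates with intervals. The 45-62% therefore describes a misreading by a user of the output. That stands: a reader might infer that a uniform effect will look heterogeneous in about half the factors, and the documents do not support so firm a statement. It needs the design HR, assumed splits, and discordant CIs taken as evidence of heterogeneity.

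A reader might also infer that separate HRs cannot show whether effects differ. That is too strong. Categories of one factor are disjoint, so the ratio of HRs and its CI follow from the planned output: subtract the log HRs and use √(SE1² + SE2²). The shortfall is a comparison that is not planned or reported, not an invalid method.

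Nor does the DN versus TN question rest only on this table. OS in TN has its own test, taken after DN. That test does not estimate the ECD contrast, however.

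Three further points stand. The 20 factors overlap: neutrophil-to-lymphocyte ratio and skin toxicity each appear twice. Prior anti-VEGF treatment may have a nearly empty level, because criterion 5b requires it where approved and available. And protocol section 10.1 leaves implementation detail to the SAP, whose version 2.0 carries no randomised-part methods. None of this supplies the missing comparison in the protocol.

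**Conclusion.** The mismatch between aim and method is real and minor. The protocol says that it will explore homogeneity and then plans nothing that compares categories, in OS for DN, OS for TN, or PFS. At the design HR with all 383 deaths and assumed splits of 50:50 to 80:20, a uniform effect gives discordant CIs in about 45-62% of two-level factors, against 5% flagged by an interaction test. The gap depends on the true effect and on how the output is read: 11-39% at a uniform HR of 0.60, and under 1% if only non-overlapping CIs count. Nothing here affects the primary or key secondary test. Because the randomised part was cancelled, the point applies to the protocol design and to any reuse of it, not to an analysis that will be run.

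**What to change.** In protocol section 10.1.2.4.2.1, for each baseline factor, add a stratified Cox model with treatment, the factor and their interaction. Report the ratio of HRs with its 95% CI and a p-value labelled exploratory. Name ECD status in the DN population as the contrast of main interest. Keep the per-category HRs for the forest plot. A factor need not be removed from the strata when it is itself the subgroup: its main effect is absorbed by the strata and the interaction remains estimable.

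The cost is a few sentences and a little programming; events, sample size and alpha do not change. The downside is about 20 overlapping, unadjusted, low-powered interaction estimates. Since 80% power needs a ratio of HRs of about 1.8-2.05, the text should say that a non-significant interaction does not establish homogeneity and that the CI on the ratio is the result to read.
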